APPENDIX C: Epic MyHealth Message for Intervention #2 (Tight Control / OB Provider Monitoring)

Dear Ms. [last name],

Thank you for being part of the Vanderbilt Fourth Trimester (V4) study. The V4 study will help us learn how to better care for women with high blood pressure in pregnancy.

You have been assigned to the following interventions:

1. Blood pressure goal: <140/90

From discharge through 6 weeks postpartum, we recommend that your blood pressure be less than 140 mmHg systolic (top number) and less than 90 mmHg diastolic (bottom number). If either the top or the bottom blood pressure is higher than the target, your obstetric provider may consider starting medications or changing your dose of medication.

2. Blood pressure monitoring: Obstetric Provider

- You will be given an appointment to have your blood pressure checked in the office within 10 days of delivery. Usually, you receive a MyHealth message about the appointment.
- For the first 2 weeks after delivery, you should check your blood pressure twice a day
- For weeks 3 to 6, you should check your blood pressure once a day
- If your blood pressures are over the goal above, contact your obstetric provider

3. Preeclampsia Danger Signs

Seek medical attention within an hour if you have any of the following:

- Blood pressure of 160 mmHg systolic (top number) or 110 mmHg diastolic (bottom number) after two blood pressure checks at least 15 minutes or more apart and within 4 hours
- A persistent headache that does not go away with rest, eating, or Tylenol
- Spots in your vision or difficulty seeing
- Difficulty breathing
- Persistent and worsening pain in your belly especially in the mid-upper or right-upper areas

4. Long-term Care

High blood pressure in pregnancy often goes away after delivery, but in some people it stays. Even if it goes away, having high blood pressure in pregnancy can make you higher risk for high blood pressure or heart disease later in life. You should see a primary care provider or cardiologist within 3 months after delivery to discuss ways to improve your heart health and to monitor your blood pressure. Be sure to tell your provider that you had high blood pressure in pregnancy.

Instructions for checking your blood pressure

1. Wait at least 30 minutes after smoking, eating, drinking caffeine (coffee, tea, soda), or exercising.
2. Sit comfortably at a table with both feet on the floor and your arm resting on the table, palm up.
3. Wrap the cuff around your arm, just above your elbow and not over clothing.
4. Push the button to inflate the cuff and record the blood pressure reading.
5. If the reading is above your goal blood pressure, wait 15 minutes and recheck it

If you have any questions or concerns about the study, please contact [name] at [contact]

APPENDIX D: Epic MyHealth Message for Intervention #3 (Standard Control / Augmented Remote Blood Pressure Monitoring)

Dear Ms. [last name],

Thank you for being part of the Vanderbilt Fourth Trimester (V4) study. The V4 study will help us learn how to better care for women with high blood pressure in pregnancy.

You have been assigned to the following interventions:

1. Blood pressure goal: <150/100

From discharge through 6 weeks postpartum, we recommend that your blood pressure be less than 150 mmHg systolic (top number) and less than 100 mmHg diastolic (bottom number). If either the top or the bottom blood pressure is higher than target, your obstetric provider may start or change medications.

2. Blood pressure monitoring: Remote Blood Pressure Monitoring

- Our Hypertension Nurse Navigator [Name] will be the primary contact for all issues related to blood pressure until 6 weeks after delivery. She will contact you through MyHealth.
- You will be given an appointment to have your blood pressure checked in the office within 10 days of delivery. Usually, you receive a MyHealth message about the appointment.
- For the first 2 weeks after delivery, you should check your blood pressure twice a day. Record your blood pressures every day in the Track My Health feature on your MyHealth app. The Hypertension Nurse Navigator will contact you every weekday to comment on your blood pressures.
- For weeks 3 to 6, you should check your blood pressure once a day unless otherwise instructed. Record your blood pressures every day in the Track My Health feature on your MyHealth app. The Hypertension Nurse Navigator will contact you at least weekly to comment on your blood pressures.
- If your blood pressures are over the goal above, you may be recommended to start medications or change your dose of medication
- The Hypertension Nurse Navigator will update your obstetric provider on your blood pressure management

3. Preeclampsia Danger Signs

Seek medical attention within an hour if you have any of the following:

- Blood pressure of 160 mmHg systolic (top number) or 110 mmHg diastolic (bottom number) after two blood pressure checks at least 15 minutes or more apart and within 4 hours
- A persistent headache that does not go away with rest, eating, or Tylenol
- Spots in your vision or difficulty seeing
- Difficulty breathing
- Persistent and worsening pain in your belly especially in the mid-upper or right-upper areas

4. Long-term Care

High blood pressure in pregnancy often goes away after delivery, but in some people it stays. Even if it goes away, having high blood pressure in pregnancy can make you higher risk for high blood pressure or heart disease later in life. You should see a primary care provider or cardiologist within 3 months after delivery to discuss ways to improve your heart health and to monitor your blood pressure. Be sure to tell your provider that you had high blood pressure in pregnancy

Instructions for checking your blood pressure

1. Wait at least 30 minutes after smoking, eating, drinking caffeine (coffee, tea, soda), or exercising.
2. Sit comfortably at a table with both feet on the floor and your arm resting on the table, palm up.
3. Wrap the cuff around your arm, just above your elbow and not over clothing.
4. Push the button to inflate the cuff and record the blood pressure reading.
5. If the reading is above your goal blood pressure, wait 15 minutes and recheck it

If you have any questions or concerns about the study, please contact [name] at [contact]

APPENDIX E: Epic MyHealth Message for Intervention #4 (Tight Control / Augmented Remote Blood Pressure Monitoring)

Dear Ms. [last name],

Thank you for being part of the Vanderbilt Fourth Trimester (V4) study. The V4 study will help us learn how to better care for women with high blood pressure in pregnancy.

You have been assigned to the following interventions:

1. Blood pressure goal: <140/90

From discharge through 6 weeks postpartum, we recommend that your blood pressure be less than 140 mmHg systolic (top number) and less than 90 mmHg diastolic (bottom number). If either the top or the bottom blood pressure is higher than the target, your obstetric provider may start or change medications.

2. Blood pressure monitoring: Remote Blood Pressure Monitoring

- Our Hypertension Nurse Navigator [Name] will be the primary contact for all issues related to blood pressure until 6 weeks after delivery. She will contact you through MyHealth.
- You will be given an appointment to have your blood pressure checked in the office within 10 days from delivery. Usually, you receive a MyHealth message about the appointment.
- For the first 2 weeks after delivery, you should check your blood pressure twice a day. Record your blood pressures every day in the Track My Health feature on your MyHealth app. The Hypertension Nurse Navigator will contact you every weekday to comment on your blood pressures.
- For weeks 3 to 6, you should check your blood pressure once a day unless otherwise instructed. Record your blood pressures every day in the Track My Health feature on your MyHealth app. The Hypertension Nurse Navigator will contact you at least weekly to comment on your blood pressures.
- If your blood pressures are over the goal above, you may be recommended to start medications or change your dose
- The Hypertension Nurse Navigator will update your obstetric provider on your blood pressure management

3. Preeclampsia Danger Signs

Seek medical attention within an hour if you have any of the following:

- Blood pressure of 160 mmHg systolic (top number) or 110 mmHg diastolic (bottom number) after two blood pressure checks at least 15 minutes or more apart and within 4 hours
- A persistent headache that does not go away with rest, eating, or Tylenol
- Spots in your vision or difficulty seeing
- Difficulty breathing
- Persistent and worsening pain in your belly especially in the mid-upper or right-upper areas

4. Long-term Care

High blood pressure in pregnancy often goes away after delivery, but in some people it stays. Even if it goes away, having high blood pressure in pregnancy can make you higher risk for high blood pressure or heart disease later in life. You should see a primary care provider or cardiologist within 3 months after delivery to discuss ways to improve your heart health and to monitor your blood pressure. Be sure to tell your provider that you had high blood pressure in pregnancy

Instructions for checking your blood pressure

1. Wait at least 30 minutes after smoking, eating, drinking caffeine (coffee, tea, soda), or exercising.
2. Sit comfortably at a table with both feet on the floor and your arm resting on the table, palm up.
3. Wrap the cuff around your arm, just above your elbow and not over clothing.
4. Push the button to inflate the cuff and record the blood pressure reading.
5. If the reading is above your goal blood pressure, wait 15 minutes and recheck it

If you have any questions or concerns about the study, please contact [name] at [contact]

APPENDIX F: Message to Obstetric Providers Intervention #1 (Standard Control / OB Provider Monitoring)

Dear [provider's name and salutation],

Your patient, [patient's name], recently delivered and her pregnancy was complicated by a hypertensive disorder of pregnancy. She is participating in the Vanderbilt Fourth Trimester (V4) Study, which is a randomized controlled trial examining different blood pressure targets and management styles for postpartum hypertension.

Ms. [patient last name] has been assigned to the standard blood pressure control group in line with current recommendations from ACOG. Her target blood pressure is **<150 mmHg systolic and <100 mmHg diastolic**.

As part of the study, your patient will:

- Receive a blood pressure cuff and be taught how to use it properly
- Be scheduled for an in-person blood pressure check within 10 days of delivery
- Be instructed to check blood pressures twice daily for weeks 1-2 after delivery and daily for weeks 3-6
- Contact you if she has blood pressures consistently above this target
- Be advised of preeclampsia danger signs and symptoms
- See you for routine postpartum needs including a postpartum visit
- Be instructed to see a primary care provider or cardiologist within 3 months of delivery

We sincerely appreciate your support for this study. If you have any questions or concerns, please do not hesitate to contact [name] at [contact].

Sincerely,

[name], MS (Primary Investigator)
Maternal-Fetal Medicine

[name] (Co-Primary Investigator)
Maternal-Fetal Medicine Fellow

APPENDIX G: Message to Obstetric Providers **Intervention #2 (Tight Control / OB Provider Monitoring)**

Dear [provider's name and salutation],

Your patient, [patient's name], recently delivered and her pregnancy was complicated by a hypertensive disorder of pregnancy. She is participating in the Vanderbilt Fourth Trimester (V4) Study, which is a randomized controlled trial examining different blood pressure targets and management styles for postpartum hypertension.

Ms. [patient last name] has been assigned to the tight blood pressure control group. Her target blood pressure is **<140 mmHg systolic** and **<90 mmHg diastolic**. We recommend initiating or titrating medications to maintain blood pressures less than 140/90.

As part of the study, your patient will:

- Receive a blood pressure cuff and be taught how to use it properly
- Be scheduled for an in-person blood pressure check within 10 days of delivery
- Be instructed to check blood pressures twice daily for weeks 1-2 after delivery and daily for weeks 3-6
- Contact you if she has blood pressures consistently above this target
- Be advised of preeclampsia danger signs and symptoms
- See you for routine postpartum needs including a postpartum visit
- Be instructed to see a primary care provider or cardiologist within 3 months of delivery

We sincerely appreciate your support for this study. If you have any questions or concerns, please do not hesitate to contact [name] at [contact].

Sincerely,

[name], MS (Primary Investigator)
Maternal-Fetal Medicine

[name] (Co-Primary Investigator)
Maternal-Fetal Medicine Fellow

APPENDIX H: Message to Obstetric Providers Intervention #3 (Standard Control / Augmented Remote Blood Pressure Monitoring)

Dear [provider's name and salutation],

Your patient, [patient's name], recently delivered and her pregnancy was complicated by a hypertensive disorder of pregnancy. She is participating in the Vanderbilt Fourth Trimester (V4) Study, which is a randomized controlled trial examining different blood pressure targets and management styles for postpartum hypertension.

Ms. [patient last name] has been assigned to the standard blood pressure control group in line with current recommendations from ACOG. Her target blood pressure is **<150 mmHg systolic and <100 mmHg diastolic**.

As part of the study, your patient will:

- Receive a blood pressure cuff and be taught how to use it properly
- Be scheduled for an in-person blood pressure check within 10 days of delivery
- Record blood pressures and send them to the study Hypertension Nurse Manager
- Have all hypertension related issues including blood pressure medications managed by the study Hypertension Nurse Manager in collaboration with Maternal-Fetal Medicine.
- Be advised of preeclampsia danger signs and symptoms
- See you for routine postpartum needs including a postpartum visit
- See a primary care provider or cardiologist within 3 months of delivery

The Hypertension Nurse Manager will send you periodic updates on your patient's hypertension progress.

We sincerely appreciate your support for this study. If you have any questions or concerns, please do not hesitate to contact [name] at [contact].

Sincerely,

[name], MS (Primary Investigator)
Maternal-Fetal Medicine

[name] (Co-Primary Investigator)
Maternal-Fetal Medicine Fellow

APPENDIX I: Message to Obstetric Providers Intervention #4 (Tight Control / Augmented Remote Blood Pressure Monitoring)

Dear [provider's name and salutation],

Your patient, [patient's name], recently delivered and her pregnancy was complicated by a hypertensive disorder of pregnancy. She is participating in the Vanderbilt Fourth Trimester (V4) Study, which is a randomized controlled trial examining different blood pressure targets and management styles for postpartum hypertension.

Ms. [patient last name] has been assigned to the tight blood pressure control group. Her target blood pressure is **<140 mmHg systolic and <90 mmHg diastolic**.

As part of the study, your patient will:

- Receive a blood pressure cuff and be taught how to use it properly
- Be scheduled for an in-person blood pressure check within 10 days of delivery
- Record blood pressures and send them to the study Hypertension Nurse Manager
- Have all hypertension related issues including blood pressure medications managed by the study Hypertension Nurse Manager in collaboration with Maternal Fetal Medicine.
- Be advised of preeclampsia danger signs and symptoms
- See you for routine postpartum needs including a postpartum visit
- See a primary care provider or cardiologist within 3 months of delivery

The Hypertension Nurse Manager will send you periodic updates on your patient's hypertension progress.

We sincerely appreciate your support for this study. If you have any questions or concerns, please do not hesitate to contact [name] at [contact].

Sincerely,

[name], MS (Primary Investigator)
Maternal-Fetal Medicine

[name] (Co-Primary Investigator)
Maternal-Fetal Medicine Fellow

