- **Interventions:** Participants will be randomized in a 1:1:1:1 ratio in permuted blocks of 4-12 to one of four interventions as summarized in **Table 1** and described in detail below. Randomization will be generated through sealedenvelope.com and allocation through REDCap. Randomization will be stratified by race.

Table 1: Summary of blood pressure (BP) interventions and factorial design

		Postpartum BP Goals	
Interventions		(C) Standard control BP <150/100	(D) Tight control BP <140/90
BP monitoring	(A) OB Provider Monitoring	(#1) Standard control Provider Monitoring	(#2) Tight control Provider Monitoring
	(B) Augmented Remote Monitoring	(#3) Standard control Remote monitoring	(#4) Tight control Remote monitoring

Blood Pressure Care Navigation

(A) *Obstetric Provider Monitoring (In-Person)*: Participants will be instructed to check their blood pressures twice a day for two weeks and daily for weeks 3-6 after delivery and report abnormal blood pressures or symptoms to their obstetric clinicians. Additional postpartum visits beyond the blood pressure check will be directed by their obstetric clinician.

(B) *Augmented Remote Blood Pressure Monitoring*: A physician investigator (fellow or attending) will place an order for "MyHealth BP Flowsheet" in the participant's chart, which triggers the Track My Health feature on MyHealth. The research assistant will demonstrate to the participant how to track blood pressures through the Track My Health feature on the MyHealth smartphone app. Blood pressure monitoring and management plan outlined below. Among women on antihypertensive medication, blood pressure tracking, monitoring, and feedback will continue until care has been transferred to a clinician who can provide long-term care.

Participant and Hypertension Program Manager responsibilities described in detail below:

Table 2. Participant and Hypertension Program Manager Responsibilities

Blood Pressure Monitoring	Participants Responsibilities	Hypertension Program Manager Responsibilities
Weeks 1-2 after delivery	
 ▶ Check blood pressures twice daily ▶ Record BPs every day in MyHealth ▶ Seek urgent care (triage, ED) for sustained severe HTN or symptoms 	
 ▶ Receive BPs notifications daily M-F ▶ Call patients who do not send BPs ▶ Adjust antihypertensive medications based on sections (C) and (D) below

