Weeks 3-6 after delivery	
 ▶ Check blood pressures once daily ▶ Record BPs daily in MyHealth ▶ Seek urgent care (triage, ED) for sustained severe HTN or symptoms 	
 ▶ Receive BPs notifications weekly ▶ Adjust antihypertensive medications based on sections (C) and (D) below
Communication with obstetric clinicians		
 ▶ Send updates on HTN management at weeks 2, 4, and 6 ▶ Document medication changes in EStar ▶ Send updates to non-VUMC obstetric clinicians with any antihypertensive medication changes
Care Handoffs	
 ▶ Schedule postpartum visit at 4-6 weeks ▶ Schedule a visit with a primary care clinician or cardiologist at month 3 	
 ▶ Ensure that postpartum visits are scheduled by 4-6 weeks ▶ Ensure that primary care or cardiology visits are scheduled at month 3 ▶ Remind patients about all visits

Blood pressure Control

(C) *Standard Blood Pressure Control*: Blood pressure targets will be <150 mmHg systolic and <100 mmHg diastolic consistent with current postpartum recommendations from ACOG. Blood pressure notifications for the HTN program navigator will reflect these parameters and medications will be initiated or titrated to meet these goals. See Appendix J for specifics on management and Appendix L for recommended medication regimens

(D) *Tight Blood Pressure Control*: Blood pressure targets will be <140 mmHg systolic and <90 mmHg diastolic. Blood pressure notifications for the HTN program navigator will reflect these parameters and medications will be initiated or titrated to meet these goals. See Appendix K for specifics on management and Appendix L for recommended medication regimens.

- ▶ **Survey 2** (6-weeks after delivery): Participants will receive the survey via text web-link or email link. Survey 2 asks questions about the participant's experience managing hypertension after delivery, the Mothers On Respect Index (MORI) and the Communication Assessment Tool geared towards postpartum care, the PROMIS Bank v1.0 Anxiety (adaptive) survey, the PROMIS Bank v1.0 Depression (adaptive) survey, the PROMIS Bank v2.0 Instrumental Support (adaptive) survey. We estimate that this survey will take 20 minutes to complete. Participants will receive a \$20 gift card for completion of this survey.

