Primary care visit attendance (%)	10%	43%
Diastolic dysfunction: Mean early diastolic filling or e' (SD)	11.7 (3.1)	1.24

DATA AND SAFETY MONITORING

Data will be entered directly into the Research Electronic Data Capture (REDCap) site, a secure web platform for building and managing online databases and surveys with flexible design of electronic CRFs. REDCap is compliant with the Health Insurance Portability and Accountability Act and includes password protection. REDCap maintains records of all changes made to databases so that investigators can identify deleted data and changes made. Each person accessing REDCap has an individual ID for security tracking and to prevent unauthorized access to data. Data can be exported to common statistical analysis packages (e.g., SAS, R, and Stata) and protected health information removed. Several internal quality checks are available in REDCap including: automatic range checks for numeric variables and creation of automatic data reports that help identify data that appears inconsistent, incomplete, or inaccurate. Every two weeks, a separate clinical trials associate assigned to support the study will audit 3 randomly selected charts to ensure that data have been entered correctly and for continuous process improvement. After obtaining informed consent, a copy of the consent form will be sent to participants via email or text and all information retained in the REDCap database. The REDCap database is encrypted and can only be accessed by research personnel with appropriate clearance.

For this study, an adverse event (AE) is defined as any untoward medical occurrence associated with the study, whether or not considered intervention- or procedure-related. An AE can therefore be any undesirable or unintended sign, symptom, laboratory testing or diagnostic imaging finding, or disease temporally associated with participation in the study, without any judgement about causality. The determination of the relationship between the AE and the study procedures must be made by the PI or their designee. This definition will also include changes in the participant medical status that may be related to the study procedures. Maternal medical conditions that are present prior to consent can be considered as baseline and not reported as AEs. However, if the participant's condition deteriorates at any time during the study, it will be recorded as an AE.

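### In both remote-monitoring arms the documents disagree on who changes blood pressure medication and on when follow-up of women on medication ends; the texts need to be reconciled

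*Combined protocol and SAP*

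**What the plan says.** **Who changes medication in the remote arms.** Table 2 makes adjustment of antihypertensives a duty of the Hypertension Program Manager, both in weeks 1-2 and in weeks 3-6. Appendices H and I tell the obstetric provider that the patient will "Have all hypertension related issues including blood pressure medications managed by the study Hypertension Nurse Manager", in collaboration with Maternal-Fetal Medicine. Item 1 of Appendix E tells the woman that if either reading is "higher than the target, your obstetric provider may start or change medications"; Appendix D says the same but for one article. Item 2 of both messages says the navigator "will be the primary contact for all issues related to blood pressure until 6 weeks after delivery".

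**How long remote follow-up lasts.** Study Procedures, intervention (B), says that for those taking antihypertensives "blood pressure tracking, monitoring, and feedback will continue until care has been transferred to a clinician who can provide long-term care". Appendices J and K give weekly monitoring from week 3 with no end. Appendices D and E limit the blood pressure goal, the recording instructions and the navigator's contact role to the first 6 weeks. Table 2's last monitoring row is weeks 3-6, and its only scheduled reports to the obstetric clinician are set by "Send updates on HTN management at weeks 2, 4, and 6". The hand-off comes later: the participant is to "Schedule a visit with a primary care clinician or cardiologist at month 3".

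**The concern.** Two questions have to be settled for any remote-monitoring arm: who acts on a reading above goal, and until when. Here the answer depends on which document is read.

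The first stake is safety. If the woman believes that her obstetric provider decides on medication, and the provider has been told that the study does, an above-goal reading may be acted on late or by both. After week 6, a woman still on medication is within the protocol's commitment to continue, but her own instructions have run out.

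The second stake is the comparison itself. Who titrates is part of what separates augmented remote monitoring (B) from obstetric provider monitoring (A). If obstetric providers also titrate in arm B, the contrast may shrink for blood pressure at 7-10 days and for severe hypertension and medication use to 6 weeks.

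**Working it through.** No power or sample-size figure is at issue, so the check is a side-by-side reading plus simple counts. I take the Program Manager, Nurse Manager and Nurse Navigator to be one role; the documents use these titles interchangeably but do not say so outright.

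**Step 1. Who changes medication, remote arms**

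| Source | Reader | Party named |
|---|---|---|
| Table 2 | Study staff | Hypertension manager |
| Appendices H, I | Obstetric provider | Hypertension manager, with Maternal-Fetal Medicine |
| Appendices D, E, item 1 | Participant | Obstetric provider |
| Appendices D, E, item 2 | Participant | Navigator as main contact; medication may be recommended, by whom not said |

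The two documents addressed to clinical staff agree. The participant's message departs from them, and its items 1 and 2 do not fit together. Item 1 closely follows the corresponding item in Appendices B and C, which belong to the provider-monitoring arms, where naming the obstetric provider is consistent.

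Table 2 sends information from the manager to the obstetric clinician. No text asks an obstetric provider who changes medication to tell the manager, so duplication is guarded against in one direction only.

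**Step 2. End of follow-up for women on medication**

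| Source | End |
|---|---|
| Intervention (B), protocol body | Transfer to a long-term clinician |
| Appendices J, K | None stated (week 3 onward) |
| Appendices D, E | 6 weeks, no exception for medication |
| Table 2, monitoring rows and clinician updates | Week 6 |
| Table 2, care hand-off | Visit at month 3 |

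Intervention (B) can be read as an exception to a general 6-week rule. That would be coherent, but neither the participant messages nor Table 2's monitoring rows carry the exception. From week 7 no row says who receives readings, and the message no longer asks for them.

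**Step 3. Size**

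- Participants affected by the medication conflict: Table 5 projects 1404 enrolled. Allocation is 1:1:1:1 and two of the four arms are remote, so 1404 × 2/4 = 702.
- Length of the unclear period: if transfer happens only at the month-3 visit (week 12-13), 12 − 6 = 6 to 13 − 6 = 7 weeks.
- Women affected by the duration conflict: the share on medication at week 6 is not in the documents. For illustration only, an assumed 20% to 50% gives 0.20 × 702 = 140 to 0.50 × 702 = 351, before any loss to follow-up. The conclusion does not rest on this range.

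**Step 4. Outcomes exposed (Table 3)**

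Unclear responsibility up to week 6 overlaps the 7-10 day blood pressure outcomes, the 3-week readmission and urgent-visit outcomes, and the 6-week severe hypertension, morbidity and medication-use outcomes. The period after week 6 overlaps only the 12-week primary care visit and the later administration of the communication questionnaire. The duration conflict is therefore mainly one of continuity and safety.

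**The case against.** The case against is that this is a wording mismatch with little practical effect, and parts of it are right.

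- **Safeguards up to week 6 are substantial.** The manager receives readings on weekdays and then weekly, calls women who send none in weeks 1-2, adjusts medication, documents changes and updates the obstetric clinician at weeks 2, 4 and 6. The woman is told to expect contact every weekday and later at least weekly. An above-goal reading handled by nobody is therefore unlikely in this period. The instruction to seek care for severe readings or danger symptoms is not part of the conflict.
- **Support does not stop at week 6.** There is a 4-6 week postpartum visit, and the manager must ensure that the month-3 visit is scheduled and send reminders.
- **The treatment algorithms are figures not reproduced here** and may say who acts. They could not cure the participant messages, which are separate texts.

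Three stronger readings are tempting and are not supported.

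- A reader might infer that remote-arm women are instructed to take high readings to their obstetric provider. They are not; that instruction appears only in Appendices B and C. Drift toward provider monitoring is possible because of item 1, but it is not directed.
- A reader might infer that women are told the study stops following them at week 6. The messages limit the navigator's role to 6 weeks and are silent after that.
- A reader might take the 10% baseline for "Primary care visit attendance" in Table 6 to mean that most remote-arm women would miss the hand-off. It is a power-calculation input, it omits cardiology visits, and it is not a forecast for arms with scheduling help and reminders.

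What stands is that neither conflict is resolved anywhere in the text.

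**Conclusion.** Both conflicts hold. The one on who changes medication is the clearer: it reaches every participant in the two remote arms, about 702 of 1404 if Table 5 is met, and it sets the participant's message against both the duty table and the letter to her provider. The one on duration concerns only women still on medication at week 6, an unknown number, over about 6 to 7 weeks if care passes only at month 3. Transfer could come earlier, since intervention (B) sets no date.

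That responsibility may be unclear or duplicated is an inference from the texts, not something they state. Any blurring of the monitoring contrast cannot be sized from the documents. The point still deserves action before the messages are used, because they give participants instructions that differ from the protocol. The documents do not settle which rule is right, and this review takes no position on it.

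**What to change.** Reconcile Study Procedures intervention (B), Table 2 and Appendices D, E, H, I, J and K as follows:

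1. Name one party responsible for medication changes in the remote arms, and make item 1 of Appendices D and E agree with Table 2 and Appendices H and I. If obstetric providers may also change medication, say so in every one of these places and state how the manager is informed.
2. State one end of remote follow-up for women on antihypertensive medication, and carry it into the goal, recording and contact lines of Appendices D and E and the monitoring schedule of Appendices J and K.
3. Add a Table 2 row for the period after week 6 that matches that rule and says who receives readings, if any are to be sent, until hand-off.

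The clinical rule in each case is the investigators' choice. The cost is wording in the appendices and one table row, with no change to randomisation, sample size or analysis. If follow-up until transfer is kept, the manager carries some women past week 6, which intervention (B) already commits the study to.
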